10.7. Derivation of secondary efficacy parameters

The minimum inhibitory concentration (MIC), the minimal parasiticidal concentration (MPC90), and the PRR48 are derived from the PD models. The MIC is defined as the concentration when parasite clearance by the drug equals the parasite growth, i.e., the time at which the minimum parasite concentration is observed. It is calculated with the following equation in case of the Emax model.

$$MIC = EC_{50} \left(\frac{GR}{E_{max} + GR} \right)^{1/Hill}$$

For the other models, the calculation is only valid at steady-state. However, an apparent MIC is determined by simulations as the concentration C_c at the time when the predicted parasite counts are at the minimum.

The MPC90 is defined as the concentration at which the clearance effect is at 90% of the maximum. It is calculated as follows for the Emax model.

$$MPC_{90} = EC_{50} \cdot 9^{1/Hill}$$

For the other models, the calculation is only valid at steady-state. However, an apparent MPC90 is determined by simulations as the blood concentration C_c at the time when the predicted clearance effect is at 90% of the maximum during the drug elimination phase. The PRR48 is defined as the parasite clearance achieved within 48 hours, usually given as the reduction of values on log10 transformed scale. The maximum capacity of parasite clearance in 48 hours is determined as follows assuming that concentrations are maintained well above the MPC90 for this time span.

$$PRR_{48} = 48h \frac{E_{max} - GR}{\ln(10)}$$

The actual PRR48 for a given dose is determined as the difference of predicted parasite levels between the time when the dose is given and 48 hours later.

Key efficacy parameters will be derived using the simulations of viable parasites in case the clearance model is selected as final model.

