10.6. Model building

10.6.1. General PKPD model building approach

Population models of the PK and PD will be developed in step-wise manner.

1. A population PK model will be developed to obtain individual PK parameter estimates based on which the individual PK profiles are described well.
2. A parasite growth model (parasite growth rate and deviation of parasitemia at inoculation from parasitemia at treatment administration) will be estimated from the total parasite counts before treatment administration. Estimation of typical and individual PD parameters will be performed with IQRtools SysFit. Other appropriate growth models, e.g. an oscillatory model, will be tested if advisable.
3. The PKPD model will be build using the individual PK parameter estimates and individual growth model parameter estimates as regression parameters. Estimation of typical and individual PD parameters will first be performed with IQRtools SysFit to investigate model identifiability and second with Monolix to additionally estimate IIV.

Estimations will be done using gradient-based SysFit algorithm in IQRtools or SAEM algorithm in Monolix. Other appropriate methods may be used if advisable.

Inter-individual variability (IIV) is implemented for normally distributed parameters using the following equation with θ_0 as population average parameter, θ_i as individual parameter, and η_i as random effect that is distributed normally around zero ($\eta_i \sim N(0, \omega^2)$).

$$\theta_i = \theta_0 + \eta_i$$

The following equation is used for log-normally distributed parameters.

$$\ln(\theta_i) = \ln(\theta_0) + \eta_i$$

Continuous covariates on log-normally distributed parameters will be implemented as follows.

$$\theta_i = \theta_0 \cdot \frac{COV_i}{COV_{median}}^\beta \cdot \eta_i$$

θ_i represents the individual parameter, θ_0 the population mean value, COV_i the individual covariate value, COV_{median} the population median covariate value, β the covariate coefficient, and η_i the individual random effect.

Categorical covariates on log-normally distributed parameters will be implemented as follows.

$$\theta_i = \theta_0 \cdot \sum_j (e^{\beta_j \cdot COV_{ij}}) \cdot \eta_i$$

The individual covariate values COV_{ij} are 1 if participant i belongs to the j^{th} category of the covariate and 0 otherwise. $\beta_{j,i}$ is the covariate value for the j^{th} category. For one category, i.e. the reference, $\beta_{j,i}$ is 0.

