10.6.3. PD modeling

PD model development will be done using gradient based algorithms in IQRTools SysFit. The selected model will then be estimated with SAEM in Monolix to allow for estimation of IIV. Other appropriate methods may be used if advisable. As a general concept the changes in living parasite P are modeled as the effect of a net exponential growth rate GR and a killing or clearance rate $Kill$ due to Pyronaridine. The initial parasitemia P_{base} at time t_0 will be derived from the mean parasitemia which was observed at treatment administration and a parameter $PLerr$ to allow for population and individual deviations. The equations are expressed in the log-scale such as:

$$\frac{dPL}{dt} = GR - Kill$$
$$PL(t_0) = PL_{base} + PL_{err}$$

where $PL = \ln(P)$ is the log-transformed parasite counts.

Three different models describing the relationship of Pyronaridine blood concentration on the killing rate will be tested:

(1) The " E_{max} -model" assumes a direct effect of concentrations on parasite killing/clearance, such as:

$$Kill = E_{max} \cdot \frac{C_c^{Hill}}{C_c^{Hill} + EC_{50}^{Hill}}$$

where C_c is the concentration in the central compartment, E_{max} is the maximum effect of the drug, EC_{50} is the concentration that results in 50% of the maximum effect and $Hill$ is the Hill coefficient.

(2) The "Turnover model" implements an indirect response model reflecting the idea that the kinetics of drug-receptor binding lead to a lagged concentration-effect relationship, such as:

$$Kill = E_{max} \cdot R$$
$$\frac{dR}{dt} = k_{in} \left(\frac{C_c^{Hill}}{C_c^{Hill} + EC_{50}^{Hill}} - R \right)$$

where k_{in} represents the binding rate of the drug to a "receptor", which results in a lag-time in the response. Furthermore, EC_{50} represents the concentration that results in a 50% occupancy of the receptor which leads to 50% of the maximum effect given enough time to reach it.

(3) The "Clearance model" assumes that the observed parasites are a mixture of living and dead parasites. The drug has a direct effect on the killing rate of the parasites, and then the parasites are cleared, but still observed. Therefore, the equations, in the normal scale, are:

$$\frac{dP_{Alive}}{dt} = P_{Alive} \cdot (GR - Kill)$$
$$\frac{dP_{Dead}}{dt} = P_{Alive} \cdot Kill - CLpara \cdot P_{Dead}$$
$$Kill = E_{max} \cdot \frac{C_c^{Hill}}{C_c^{Hill} + EC_{50}^{Hill}}$$
$$P_{obs} = P_{Alive} + P_{Dead}$$
$$P_{Dead}(t_0) = 0$$

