where $CLpara$ is the clearance rate of dead parasites, and P_{obs} is the count of measured parasite. If viable parasitemia is available then it is possible to differentiate between the killing rate and the clearance rate. Otherwise, both populations are measured indistinguishably, and E_{max} is fixed to the *in vitro* E_{max} value for this model.

During base model building, the Hill coefficient may not be identifiable. Then the best value for the Hill coefficient will be determined by estimating models with fixed Hill coefficients and selecting the best model based on the Bayesian information criterion (BIC). Considered Hill coefficients are 1, 2, 3, 5, 7, and 10. If covariate modeling is performed, the Hill coefficient is fixed in the value determined in the base model building.

IIV will be assumed on all parameters but the Hill coefficient. Parameters are assumed to be log-normally distributed besides the log-transformed deviation from the baseline parasitemia value $PLerr$ for which normal distribution will be assumed. The standard deviation of the IIV will be fixed to 0.2 for the SysFit approach. When parameters are estimated with Monolix, standard deviations of the IIV will be estimated.

Using the SysFit approach for PD modelling, parameter estimation will be started from 24 initial guesses. Identifiability of the best fit will be analysed using the profile likelihood method.

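### The MIC formula has Emax + GR where the plan's own model gives Emax − GR, so the reported MIC would be too low and parasites would still be growing at it

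*SAP*

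**What the plan says.** SAP 10.7 gives the definition in words: "The MIC is defined as the concentration when parasite clearance by the drug equals the parasite growth". For the Emax model it supplies a closed form, "MIC = EC_{50} \left(\frac{GR}{E_{max} + GR} \right)^{1/Hill". Protocol 9.4.2 carries the same definition and the same equation, and lists the MIC among the key parameters derived within the primary-endpoint analysis.

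The model behind it is in SAP 10.6.3 and Protocol 9.4.2. Log parasitaemia changes at rate GR − Kill, with "Kill = E_{max} \cdot \frac{C_c^{Hill}}{C_c^{Hill} + EC_{50}^{Hill" and an EC50 that "is the concentration that results in 50% of the maximum effect". The companion formulas in SAP 10.7 are "PRR_{48} = 48h \frac{E_{max} - GR}{\ln(10" and "MPC_{90} = EC_{50} \cdot 9^{1/Hill".

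SAP 10.6.3 also tests a turnover model and a clearance model. For these, SAP 10.7 treats the closed form as valid only at steady state and takes an apparent MIC from simulation, as the concentration at the predicted parasite minimum.

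SAP 10.6.1 sets out how covariates enter. The categorical case is introduced with "Categorical covariates on log-normally distributed parameters will be implemented as follows".

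**The concern.** The definition and the closed form in SAP 10.7 cannot both be right. The MIC is the point where the net rate GR − Kill is zero. The printed expression gives a lower concentration, at which the net rate is still positive. Because the error always runs the same way, pyronaridine would look more potent than the fitted model says it is. Protocol 2.1 states that the study data are meant to inform partner-drug choice and dosing for new combinations, and a threshold that understates the concentration needed to hold parasites in check is a misleading input to that.

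The covariate equations in SAP 10.6.1 have a separate defect. They multiply by the random effect itself, which is centred on zero, and so contradict the log-normal form given just above them.

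**Working it through.** **Inputs.** The definition (Kill = GR) is from SAP 10.7. The dynamics and kill function are from SAP 10.6.3 and Protocol 9.4.2. Neither document gives values for Emax or GR, so those below are assumptions. The Hill values are those in SAP 10.6.3: "Considered Hill coefficients are 1, 2, 3, 5, 7, and 10".

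**Step 1: solve the definition.** Write H for Hill.

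Emax × C^H / (C^H + EC50^H) = GR

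C^H × (Emax − GR) = GR × EC50^H

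MIC = EC50 × (GR/(Emax − GR))^(1/H), which exists only if Emax > GR.

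**Step 2: put the printed MIC back into the model.** The printed form means C^H = EC50^H × GR/(Emax + GR). Then Kill = Emax × GR/(Emax + 2GR), which is below GR. The net rate is GR − Kill = 2GR²/(Emax + 2GR), positive for every Hill value.

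**Step 3: limiting case.** If Emax = GR, no finite concentration stops growth. The printed formula still returns 0.5^(1/H) × EC50.

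**Step 4: is another convention intended?** The PRR48 formula subtracts GR from Emax, and the MPC90 formula gives exactly Kill = 0.9 × Emax. Both treat Emax as the gross kill rate. If Emax were instead the net maximum (gross = Emax + GR), solving Kill = GR would give EC50 × (GR/Emax)^(1/H), which is not the printed form either.

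**Step 5: size.** Printed/correct MIC = ((Emax − GR)/(Emax + GR))^(1/H). The 48 h rise at the printed MIC is exp(48 × 2GR²/(Emax + 2GR)).

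| Assumed Emax, GR (/h) | Hill 1 | Hill 2 | Hill 3 | Hill 5 | Hill 7 | Hill 10 | 48 h rise at printed MIC |
|---|---|---|---|---|---|---|---|
| 0.15, 0.07 | 0.36 | 0.60 | 0.71 | 0.82 | 0.87 | 0.90 | 5.1-fold |
| 0.20, 0.07 | 0.48 | 0.69 | 0.78 | 0.86 | 0.90 | 0.93 | 4.0-fold |
| 0.20, 0.05 | 0.60 | 0.77 | 0.84 | 0.90 | 0.93 | 0.95 | 2.2-fold |
| 0.30, 0.03 | 0.82 | 0.90 | 0.94 | 0.96 | 0.97 | 0.98 | 1.3-fold |

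For the second row: 0.13/0.27 = 0.48; net rate 2 × 0.0049/0.34 = 0.0288/h; exp(48 × 0.0288) = 4.0.

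The design gives a rough anchor for GR. About 2,800 viable parasites are inoculated, and more than 5,000/mL is expected on Day 8 (192 h). With an assumed 5 L blood volume, the start is 0.56/mL, and ln(5000/0.56)/192 = 0.047/h as a minimum average (0.046 to 0.048 for 4 to 6 L). With GR 0.047 and an assumed Emax of 0.20, the ratio is 0.153/0.247 = 0.62 at Hill 1 and 0.85 at Hill 3, with about a 2-fold rise in 48 h.

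**Step 6: check against the simulated nadir.** With Emax 0.20, GR 0.05, Hill 3 and the 14-day half-life in Protocol 2.1, the simulated concentration at the parasite minimum is 0.693 × EC50. The minus form gives (0.05/0.15)^(1/3) = 0.693; the printed form gives (0.05/0.25)^(1/3) = 0.585. The concentration would reach the printed MIC 336 h × ln(0.25/0.15)/(3 × ln 2) = 82.5 h after the true nadir.

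**Step 7: covariate equations (SAP 10.6.1).** The log-normal form there implies theta_i = theta_0 × exp(eta_i), but both covariate equations multiply by eta_i, which has mean zero. In the categorical equation, with K categories, a reference participant contributes exp(0) = 1 from every term, so the sum is K and the typical value becomes K × theta_0 instead of theta_0.

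**The case against.** The error is conditional. It matters only if the direct Emax model is selected and the code copies the printed sign. The verbal definition is right, the code is not visible, and the other two models take their MIC from simulation. This stands as a limit on scope, but a pre-specified formula should be correct for the case it covers.

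The MIC is also derived after estimation. EC50, Emax, Hill and GR are unaffected, as are MPC90 and PRR48, and the patient simulations in SAP 10.8 do not list the MIC as an output. SAP 10.7 files it under secondary efficacy parameters. All of this is fair. Even so, Protocol 9.4.2 names the MIC as a key parameter within the primary-endpoint analysis, so it will be reported and used.

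The size depends on unknown rates and can be slight. Over Emax 0.15 to 0.50/h, GR 0.03 to 0.07/h and Hill 1 to 10, the understatement runs from about 1% to 64%. That range should be quoted whole. The direction does not vary, and growth at the printed MIC does not depend on Hill.

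The plan makes no comparison of MICs across models, so loss of comparability between the closed-form and simulated values is a minor point.

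The covariate equations may be only a notation slip, since the correct log-normal form stands nearby and covariates are optional. They are secondary, and the conclusion on the MIC does not rest on them.

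A text-extraction fault is unlikely: the plus sign appears in both documents, while the minus sign in PRR48 was read correctly.

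**Conclusion.** The concern holds. The closed-form MIC in SAP 10.7 and Protocol 9.4.2 contradicts its own definition and model. This is algebra and needs no assumption. If the Emax model is selected and the formula is applied as printed, the MIC is understated whenever Emax > GR, and parasites are still multiplying at it. Only the size rests on assumed rates: roughly half the correct value in an unfavourable but plausible case (Emax 0.20/h, GR 0.07/h, Hill 1), shrinking to a few percent at high Hill or low GR/Emax. It should be corrected before the analysis is run. The covariate equations are also wrong as printed, with no effect on the MIC algebra.

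**What to change.** In SAP 10.7 and Protocol 9.4.2, replace the equation with MIC = EC50 × (GR/(Emax − GR))^(1/Hill), and state that it is defined only when Emax > GR. Add two checks to the modelling code: Kill evaluated at the reported MIC equals GR, and the closed form agrees with the simulated nadir concentration under the Emax model. Record the correction in SAP section 13, which at present reports no changes.

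In SAP 10.6.1, write theta_i = theta_0 × (COV_i/COV_median)^beta × exp(eta_i) for continuous covariates and theta_i = theta_0 × exp(sum over j of beta_j × COV_ij) × exp(eta_i) for categorical ones.

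The cost is small: wording in the SAP and in the Modelling Analysis Plan if it repeats the equation, probably one line of code, and no new data. The protocol edit needs investigator, sponsor and ethics committee agreement under Protocol 10.1.2. Where the code had used the printed form, the reported MIC will be higher and so less favourable.

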10.8. Post-hoc Analysis

Simulations of clinical efficacy parameters and endpoints in African children

Simulations will be performed using the already available PK model established and patients Simulations will be performed for 1, 2 and 3 daily dose regimens at the adult equivalent 720mg Pyronaridine tetraphosphate. For each dose level, 200 trials with 625 participants will be performed. Dose levels, number of trials and number of participants may be adjusted if advisable. For each trial a new set of population parameters will be sampled from the uncertainty distribution and individual parameters were sampled from the IIV. The covariates age, body weight and baseline parasitemia will be sampled from a clinical dataset of real patients.

The baseline parasitemia in patients are typical 1000 fold higher than in challenge participants and in the range of 10^4 p/uL

The following parameters will be calculated (median and 95%CI):

- Cmax: maximum Pyronaridine blood concentration
- AUC: Area under the Pyronaridine blood concentration curve

- PRR48: Parasite reduction ratio after 48h
- Parasite clearance time: time to reach the microscopic LOD (10 p/uL)
- ETF CSoff: Early treatment failure clinical symptoms off; Parasitemia on day 2 higher than on day 0, irrespective of axillary temperature, or, parasitemia on day 3, or, parasitemia on day 3 $\geq 25\%$ of count on day 0.
- ETF CSon: Early treatment failure clinical symptoms on; Parasitemia on day 2 higher than on day 0, irrespective of axillary temperature, or, parasitemia on day 3 $\geq 25\%$ of count on day 0.
- LCF28: Late clinical failure at day 28: Parasitemia above LLOQ on any day between day 4 and day 28 in patients who did not previously meet any of the criteria of ETC CSon.
- LPF28 CSoff: Late parasitological failure at day 28 clinical symptoms off: Parasitemia above LLOQ on any day between day 7 and day 28 with axillary temperature $< 37.5^{\circ}\text{C}$ in patients who did not previously meet any of the criteria of ETF CSoff.
- LPF28 CSon: Late parasitological failure at day 28 clinical symptoms on: Parasitemia above LLOQ on any day between day 7 and day 28 with axillary temperature $< 37.5^{\circ}\text{C}$ in patients who did not previously meet any of the criteria of ETF CSon or LCF28.
- APR28 CSoff: Adequate parasitological response at day 28 clinical symptoms off; Absence of parasitemia on day 28 irrespective of axillary temperature, in patients who did not previously meet any of the criteria of ETF CSoff or LPF28 CSoff.
- APR28 CSon: Adequate parasitological response at day 28 clinical symptoms on; Absence of parasitemia on day 28 irrespective of axillary temperature, in patients who did not previously meet any of the criteria of ETF CSon or LCF28 or LPF28 CSon.

10.9. Presentation of Results

A statistical and graphical analysis of the data (based on the general analysis dataset will include tables and figures listed in Appendix, Table A.

The analysis results will be reported in the main body of the CSR and technical details will be reported as an appendix (referred to here as the 'technical appendix'). The technical appendix will include the clinical data used in the analysis, data assembly, modelling methods, all results, discussions, and conclusions.

Key results will include description and interpretation of the selected model, parameter estimates, and diagnostic plots of goodness-of-fit and simulations and will be included in the main text. Limitations of the model prediction will be discussed in the Discussion section of the technical appendix and mentioned in the main text of the CSR.

11. SECONDARY ENDPOINTS ANALYSIS

11.1 PD Analysis

Analysis Set: PD Analysis Set

11.1.1 Data Handling

Handling of replicates

The data will be recorded as triplicate parasitaemia and duplicate gametocytaemia values for each subject at each timepoint. The replicate data will be summarised by calculating the geometric mean of the parasitaemia and parasite life-stage data (i.e. gametocytemia and ring-stage parasites) values per subject and timepoint, and will be log10 transformed for statistical analyses.

For any replicates that were non-detects (ND), the value will be substituted with 1 parasite/mL prior to calculating the geometric mean for parasitemia quantified from qPCR 18s, or as the LOD/2 of the assay for parasite life-stage data (i.e. gametocytemia and ring-stage parasites).

11.1.2 Parasite clearance kinetics

The Parasite Reduction Ratio (PRR) and corresponding parasite clearance half-life (PCt_{1/2}) of asexual parasites is derived from the clearance rate of parasitaemia after administration of pyronaridine treatment. The analysis of PD response to investigational antimalarial therapy consists of:

- calculating the optimal parasite clearance rate (slope coefficient from the log-linear decay regression of qPCR data) for each individual, then,
- estimating dose specific parasite clearance rate and 95% confidence interval (CI) by calculating the weighted average slope estimate and corresponding standard error (SE) using an inverse-variance method.

The data used for all model selection and fitting calculations is comprised of the log₁₀ transformed geometric mean of parasitaemia per timepoint per participant up to the first timepoint all parasitaemia replicates are ND. If during initial parasite clearance there are no samples ND for a participant, the last timepoint included in the analyses will be three timepoints after the minimum observed parasitemia value. All subsequent timepoints are set to 'missing' regardless of whether parasitaemia values increased afterwards due to potential recrudescence. Sensitivity analyses may be performed using other thresholds to determine parasite clearance, for example, but not limited to, the lower limit of quantification (LOQ) (i.e. the lower limit of the reportable range) of 32 parasites/mL or limit of detection of 111 parasites/mL [1], to assess robustness of PRR estimates.

The PRR per 48 hours, PRR₄₈, for asexual parasite will be estimated using the slope of the optimal fit of the log-linear relationship of the parasitaemia decay over time from pyronaridine administration for each individual, as detailed in CTM QIMR SOP 41 and Marquart et al. [8].

Table 1: Symbols and definitions of terms used in parasite clearance analysis (Part 1)

Symbol	Definition
PRR _{48,i}	Individual specific Parasite Reduction Ratio per 48 h
PRR _{48,D}	Dose specific Parasite Reduction Ratio per 48 h
$\beta_{1,i}$	Slope coefficient of log10 parasitaemia vs. time profile for individual i
SE $_{\beta_{1,i}}$	SE corresponding to $\beta_{1,i}$ for individual i
$\bar{\beta}_{1,D}$	Dose specific average slope estimate
SE($\bar{\beta}_{1,D}$)	Weighted SE of dose specific average slope estimate
PCt _{1/2}	Parasite clearance half-life

Regression Modelling to Determine Optimal Fit

A regression modelling approach to remove potential lag and/or tail phases of the parasitaemia decay profile will be used to determine the optimal log-linear decay regression. The algorithm considers removing parasitaemia data points in an iterative process from both ends of the parasitaemia curve, i.e. a combination of right censoring (removing values from the tail phase) and left censoring (removing values from the lag phase), and uses model selection techniques to find the optimal log-linear regression.

The algorithm to obtain the log-linear decay for each participant is based on the log-linear regression detailed in Equation (1), where Time is the number of hours since administration of antimalarial treatment ($Time = 1, \dots, m$), and β_0 and β_1 are the intercept and slope estimates, respectively.

$$\log_{10} Parasitemia = \beta_0 + \beta_1 Time \quad (1)$$

Based on the parasitaemia data for each participant, the iterative algorithm to determine the optimal log-linear decay for each participant is summarised in Table 2. The iterative algorithm is continued until a minimum of four observations are available.

The optimal log-linear regression model for a participant is deemed an appropriate fit if the overall model p-value < 0.001 .

Table 1: Iteration process to determine the optimal log-linear decay curve.

Step 1: For each participant, fit the full model - fit a linear regression (as defined by Equation 1) to all m parasitaemia values of participant i

Step 2: Fit two models:

- (a) Fit linear regression model to $m - 1$ parasitaemia values, removing the first observation.
- (b) Fit linear regression model to $m - 1$ parasitaemia values, removing the last observation.

Step 3: Determine the best model of Step 2(a) and Step 2(b), defined as the model corresponding to the minimum overall model p-value.

Step 4: Of the best model defined in Step 3, repeat Step 2 and Step 3 in an iterative process until a minimum of four observations.

Step 5: Of the $m - 3$ best models selected per iteration (including the full model (Step 1)), the optimal model was defined by the minimum overall model p-value.

Estimating Participant Specific PRR

The slope and corresponding SE estimate of the optimal linear regression model is used to calculate the participant specific PRR_{48} estimate and corresponding 95% confidence interval (95% CI), as shown in Equation (2) and (3), respectively.

$$PRR_{48,i} = 10^{-48 \times \beta_{1,i}} \quad (2)$$

$$95\% \text{ CI: } 10^{-48(\beta_{1,i} \pm 1.96 \times SE(\beta_{1,i}))} \quad (3)$$

where $\beta_{1,i}$ and $SE_{\beta(1,i)}$ are the slope and corresponding standard error of the slope parameter of the optimal linear regression model, respectively.

Estimating Dose Specific PRR (PRR_{48,D})

Of the s participants with appropriate overall fit ($p < 0.001$), the average PRR_{48} and corresponding 95% CI for each cohort is estimated by using the inverse variance method to calculate the weighted average linear regression slope ($\bar{\beta}_1$) and corresponding SE. The weighted average slope for s participants in the dose with appropriate overall fit is given by Equation (4):

$$\bar{\beta}_1 = \frac{\sum_{i=1}^s (w_i \times \beta_{1,i})}{\sum_{i=1}^s w_i}, \quad i = 1, \dots, s \quad (4)$$

where the weight is the inverse of the squared standard error, $w_l = \frac{1}{SE(\beta_{1,l})^2}$. The standard error of $\bar{\beta}_1$ is estimated as, $SE(\bar{\beta}_1) = \sqrt{\frac{1}{\sum_{l=1}^s w_l}}$.

Therefore the dose specific PRR (PRR_{48,D}) and corresponding 95% confidence interval is estimated as shown in Equation (5) and (6), respectively:

$$PRR_{48,D} = 10^{-48 \times \bar{\beta}_1} \quad (5)$$

$$95\% CI: 10^{-48 \times (\bar{\beta}_1 \pm 1.96 \times SE(\bar{\beta}_1))} \quad (6)$$

Parasite Clearance Half Life

The parasite clearance half-life (PCt_{1/2}) will be derived from the optimal decay rate. The relationship between PRR₄₈ and parasite clearance half-life (PCt_{1/2}) is a simple transformation of the PRR₄₈ as shown in Equation (7):

$$PCt_{1/2} = \log_{10}(2) \times \left(\frac{48 \text{ hours}}{\log_{10}(PRR_{48,l})} \right) = \frac{\log_{10}(2)}{-\beta_{1,l}} \quad (7)$$

where PRR_{48,i} is the parasitaemia ratio estimated over a 48-hour interval that is subsequently transformed into a per hour clearance rate.

Comparison of Dose Specific PRR₄₈

To determine whether there are differences between dose specific PRRs, an omnibus test for between group differences is used. The test is used to assess whether there are differences in the weighted mean slope of the J doses, using the test statistic shown in Equation (8),

$$Q_B = \sum_{j=1}^J w_{j.} (\bar{\beta}_{j.} - \bar{\beta}_{..})^2 \sim \chi_{J-1}^2 \quad j = 1, \dots, J \quad (8)$$

The weight for the j^{th} dose is denoted by $w_{j.} = \sum_{i=1}^{s_j} w_{ij}$ for participant i with appropriate overall fit in dose j . The $\bar{\beta}_{j.}$ is the weighted average slope for dose j as defined in Equation (9), and $\bar{\beta}_{..}$ is the weighted grand mean given by:

$$\bar{\beta}_{..} = \frac{\sum_{j=1}^J w_{j.} \bar{\beta}_{j.}}{\sum_{j=1}^J w_{j.}} \quad (9)$$

Post-hoc pair-wise comparisons can be calculated using the test statistic $Z_G = \frac{G}{\sqrt{v_G}}$, where G is the contrast ($G = c_1 \bar{\beta}_1 + \dots + c_J \bar{\beta}_J$) and v_G is the variance of the contrast ($v_G = \frac{c_1^2}{w_{1.}} + \dots + \frac{c_J^2}{w_{J.}}$). The p-value of the L pair-wise comparisons can be calculated using the Scheffe method, by comparing Z_G^2 to a chi-squared distribution with $L - 1$ degrees of freedom.

Parasite Regrowth

Incidence of parasite regrowth will be reported as the number and percentage of participants in each dose group, with regrowth defined as ≥ 5000 parasites/mL and a two-fold parasitaemia increase within 48 hours after initial reduction in parasitaemia.

